### 7.2 PARTICIPANT DISCONTINUATION/WITHDRAWAL FROM THE STUDY

The reason and date of any study withdrawal will be documented in the study record.

Participants who sign the informed consent form but do not receive tolebrutinib may be replaced and followed in the non-tolebrutinib cohort.

# 7.3 LOST TO FOLLOW-UP

A participant will be considered lost to follow-up if he or she fails to return for two scheduled visits and is unable to be contacted by the study site staff after 3 attempts.

The following actions must be taken if a participant fails to return to the clinic for a required study visit:

- An investigator or designee will attempt to contact the participant within 1 month to reschedule the missed visit, counsel the participant on the importance of maintaining the assigned visit schedule, and ascertain if the participant wishes to and/or should continue in the study.
- Before a participant is deemed lost to follow-up, the investigator or designee will make every effort to regain contact with the participant. These contact attempts should be documented in the participant's medical record or study file.
- Should the participant continue to be unreachable, he/she will be considered to have withdrawn from the study with a primary reason of lost to follow-up.

### 8 STUDY ASSESSMENTS AND PROCEDURES

### 8.1 SCREENING PROCEDURES

Candidates for this study are screened under the natural history protocol 89-N-0045. Data collected during screening may be used for baseline measurements and/or combined with data collected in this protocol for exploratory analyses. Screening procedures/evaluations must be performed within 6 months prior to enrollment. Screening will occur only after the participant has signed the consent for 89-N-0045.

### 8.2 EFFICACY ASSESSMENTS

Assessments are performed according to the Schedule of Activities, Section 1.3. In the event that data or samples are found to be technically inadequate for a particular procedure, procedures in Section 8.2 may be repeated twice.

### 8.2.1 Clinical Evaluations

*History and physical.* This is a targeted history and neurological examination to allow calculation of the Expanded Disability Status Scale and Scripps Neurological Rating Scale and must be performed by a credentialed provider.

*Clinical disability scales.* These include, but are not limited to, 9-hole peg test (9HPT), timed 25- foot walk (T25W), and symbol digit modalities test (SDMT). The paced auditory serial addition test (PASAT) and timed up-and-go (TUG) tests may also be performed.

*Magnetic resonance imaging.* Details regarding the use of MRI are further described in Section 6.1.1. For women of childbearing age, urine or serum pregnancy testing is performed prior to initial study drug dosing and to all MRI scans.

#### 8.2.2 Biospecimen Evaluations

Not applicable.

### 8.2.3 Correlative Studies for Research

Research blood work, cerebrospinal fluid, and urine testing are used for exploratory outcomes in this study.

*Research blood work and urine.* In addition to samples sent to the NIH Clinical Center lab for safety evaluation (Section 8.3), up to 150 ml of whole blood, as well as a urine sample, may be collected at each study visit for research purposes and processed in the NINDS Viral Immunology Section and/or Translational Neuroradiology Section. The amount of blood that may be drawn for research purposes will not exceed 10.5 mL/kg or 550 mL, whichever is smaller, over any 8-week period.

**Research lumbar puncture.** Lumbar puncture may be performed at the bedside or under fluoroscopy if required for scheduling or if judged by the study team to be in the best interest of the participant. In addition to samples sent to the NIH Clinical Center lab for safety evaluation (Section 8.3), up to 25 ml of CSF are collected for research purposes and processed in the NINDS Viral Immunology Section and/or Translational Neuroradiology Section.

Research assays are focused primarily on immune-cell subsets and their products and may include, but are not limited to, flow cytometry and protein measurements (e.g. ELISA, MesoScale, Single Molecule Array, mass spectrometry). Bulk and single-cell and/or single-nucleus RNA sequencing assays, as well as epige-netic assays (e.g. ATAC-Seq), may also be performed. Assays to assess products of glia and neurons (e.g. neurofilament light chain) may also be developed and performed. Specimens are preserved and patched for subsequent analysis whenever possible, but some assays (e.g. flow cytometry and single-cell RNA sequencing) may require use of fresh samples. Cell lines are not expected to be created as part of this protocol, but they may be created for further exploratory analyses.

8.2.4 Samples for Genetic/Genomic Analysis

Not applicable.

### 8.3 SAFETY AND OTHER ASSESSMENTS

*History and physical.* Interval history is obtained at visits over the course of the study to assess for adverse events. Focused neurological and additional portions of the physical examination are performed if clinically warranted or to follow up on any issues reported. These procedures are performed by a credentialed provider.

*Vital signs.* Temperature, pulse, blood pressure, and respiratory rate are assessed and recorded in the study record.

*Electrocardiogram (ECG)*. A 12-lead ECG is obtained using an ECG machine that automatically calculates the heart rate and measures PR, QRS, QT, and QTc intervals. At least one longer rhythm monitoring recording should be part of each ECG testing.

*Magnetic resonance imaging.* MRI is obtained without intravenous administration of an FDA-approved gadolinium-based contrast agent. However, an FDA-approved, gadolinium-based contrast agent may be given for clinical purposes (for example to investigate new neurological symptoms), if judged warranted by the evaluating clinician and provided that there are no contraindications for the subject to receive a contrast agent. Details regarding the use of MRI are further described in Section 6.1.1. For women of childbearing age, urine or serum pregnancy testing is performed prior to initial study drug dosing and to all MRI scans. MRI scans will be read by a neuroradiologist and a report entered into the NIH clinical system.

*Laboratory work.* Blood and urine samples will be sent to the NIH Clinical Center lab as per study schedule, or they may be evaluated at an outside facility. For the tolebrutinib cohorts, lab work should include complete blood count with differential (including lymphocyte subsets), blood chemistry, to include liver function tests, and ferritin, transferrin, amylase, lipase, JCV Ab, JCV PCR (blood and urine), and quantitative immunoglobulins. Serum iron panel (iron, ferritin, transferrin saturation, TIBC – total iron-binding capacity), QuantiFERON® TB Gold Test, serology for hepatitis and/or confirmatory testing, HIV and other infectious diseases to confirm inclusion and exclusionary conditions may be performed at baseline and throughout the protocol as required. TBNK assays may be performed at the time of 7T MRI for the tolebrutinib cohorts. For the control cohort, lab work should include complete blood count with differential (including lymphocyte subsets), blood chemistry as needed for MRI, JCV Ab, JCV PCR (blood and urine), and quantitative immunoglobulins. "Safety labs," as designated in the Schedule of Activities, include complete blood count and blood chemistry including liver function tests. "Liver-specific safety labs" refer to liver function tests (AST, ALT, alkaline phosphatase, and total bilirubin). Additional labs may be ordered when clinically indicated.

*Lumbar puncture.* Lumbar puncture may be performed at the bedside or under fluoroscopy if required for scheduling or if judged by the study team to be in the best interest of the participant. Samples are sent to the NIH Clinical Center lab for cell count, protein, and glucose.

Assessment of study intervention adherence. See Study Intervention Compliance, Section 6.4.

*Assessment of adverse events.* Adverse events, including serious adverse events, will be followed up as clinically warranted, including possibly by telephone or other method of communication and additional visits to the NIH.

Clinically relevant results of laboratory or radiological evaluations performed in this protocol will be provided to participants, along with a recommendation for next step (including potential follow- up at NIH or elsewhere).

In the event that circumstances beyond our control preclude the travel of one or more of the study participants to the NIH Clinical Center for a visit, or otherwise would put their health at greater risk (i.e. epidemic or pandemic), we will endeavor to establish capabilities for remote visits (using NIH approved platforms). Specifically, for safety visits, the study team will arrange for local laboratory studies to be done, and conduct a telehealth visit with the participant. Unscheduled visits, due to safety, may also be conducted remotely through telehealth and/or offsite laboratory and radiologic studies and/or in conjunction with a local physician with the guidance of the study PI and medically responsible investigator. The laboratory studies may be performed through LabCorp, Quest, or with the local physician, and results will be sent to the study team for safety monitoring and oversight. Radiology studies will be arranged through a local, non-study physician, or directly by the study team, at a site close to the participants home area if

43

travel to the NIH is not possible.

#### 8.4 ADVERSE EVENTS AND SERIOUS ADVERSE EVENTS

#### 8.4.1 Definition of Adverse Event

Adverse event means any untoward medical occurrence associated with the use of an intervention in humans, whether or not considered intervention-related (21 CFR 312.32 (a)). The descriptions and grading scales found in the revised NCI Common Terminology Criteria for Adverse Events (CTCAE) version 5.0 will be utilized for AE reporting.

### 8.4.2 Definition of Serious Adverse Events (SAE)

An adverse event (AE) or suspected adverse reaction is considered "serious" if, in the view of either the investigator or sponsor, it results in any of the following outcomes: death, a life- threatening adverse event, inpatient hospitalization or prolongation of existing hospitalization, a persistent or significant incapacity or substantial disruption of the ability to conduct normal life functions, or a congenital anomaly/birth defect. Important medical events that may not result in death, be life-threatening, or require hospitalization may be considered serious when, based upon appropriate medical judgment, they may jeopardize the participant and may require medical or surgical intervention to prevent one of the outcomes listed in this definition. Examples of such medical events include allergic bronchospasm requiring intensive treatment in an emergency room or at home, blood dyscrasias or convulsions that do not result in inpatient hospitalization, or the development of drug dependency or drug abuse.

#### 8.4.3 Classification of an Adverse Event

#### 8.4.3.1 Severity of Event

For adverse events (AEs) not included in the protocol defined grading system, the following guidelines will be used to describe severity.

- **Mild** Events require minimal or no treatment and do not interfere with the participant's daily activities.
- **Moderate** Events result in a low level of inconvenience or concern with the therapeutic measures. Moderate events may cause some interference with functioning.
- Severe Events interrupt a participant's usual daily activity and may require systemic drug therapy or other treatment. Severe events are usually potentially life-threatening or incapacitating. Of note, the term "severe" does not necessarily equate to "serious."

#### 8.4.3.2 Relationship to Study Intervention

All adverse events (AEs) must have their relationship to study intervention assessed by the investigator who examines and evaluates the participant based on temporal relationship and his/her clinical judgment. The degree of certainty about causality will be graded using the categories below. In a clinical trial, the study product must always be suspect.

- **Definitely Related** There is clear evidence to suggest a causal relationship, and other possible contributing factors can be ruled out. The clinical event, including an abnormal laboratory test result, occurs in a plausible time relationship to study intervention administration and cannot be explained by concurrent disease or other drugs or chemicals. The response to withdrawal of the study intervention (dechallenge) should be clinically plausible. The event must be pharmacologically or phenomenologically definitive, with use of a satisfactory rechallenge procedure if necessary.
- **Probably Related** There is evidence to suggest a causal relationship, and the influence of other factors is unlikely. The clinical event, including an abnormal laboratory test result, occurs within a reasonable time after administration of the study intervention, is unlikely to be attributed to

concurrent disease or other drugs or chemicals, and follows a clinically reasonable response on withdrawal (dechallenge). Rechallenge information is not required to fulfill this definition.

- **Possibly Related** There is some evidence to suggest a causal relationship (e.g., the event occurred within a reasonable time after administration of the trial medication). However, other factors may have contributed to the event (e.g., the participant's clinical condition, other concomitant events). Although an AE may rate only as "possibly related" soon after discovery, it can be flagged as requiring more information and later be upgraded to "probably related" or "definitely related," as appropriate.
- Unlikely to Be Related A clinical event, including an abnormal laboratory test result, whose temporal relationship to study intervention administration makes a causal relationship improbable (e.g., the event did not occur within a reasonable time after administration of the study intervention) and in which other drugs or chemicals or underlying disease provides plausible explanations (e.g., the participant's clinical condition, other concomitant treatments).
- Not Related The AE is completely independent of study intervention administration, and/or evidence exists that the event is definitely related to another etiology. There must be an alternative, definitive etiology documented by the clinician.

#### 8.4.3.3 Expectedness

An AE will be considered unexpected if the nature, severity, or frequency of the event is not consistent with the risk information previously described for the study intervention in the protocol or IB, according to FDA guidance (https://www.fda.gov/regulatory-information/search-fda-guidance-documents/safety-reporting-requirements-inds-investigational-new-drug-applications-and-babe). Events described in the literature, but not in the protocol or IB, will be considered unexpected for the purpose of this reporting. The PI will make the initial determination, along with the IMM. The NINDS DSMB will make final decisions of expectedness and relatedness in conjunction with the Sponsor, normally at the time of routine DSMB review. For all SAEs and high-grade AEs (AE grade 3 or above), the DSMB will come to a determination of expectedness and relatedness within ideally within 48 hours, but no more than within 7 days, of notification by the PI.

All SAEs/SUSARS will be reported to the Study Sponsor or his delegate. Form 3500 (MedWatch) may be used for all potential SUSARs submitted to the Study Sponsor.

### 8.4.4 Time Period and Frequency for Event Assessment and Follow-Up

The occurrence of an adverse event (AE) or serious adverse event (SAE) may come to the attention of study personnel during study visits and interviews of a study participant presenting for medical care, or upon review by a study monitor.

All AEs including local and systemic reactions not meeting the criteria for SAEs will be captured on the appropriate case report form (CRF). Information to be collected includes event description, time of onset, clinician's assessment of severity, relationship to study product (assessed only by those with the training and authority to make a diagnosis), and time of resolution/stabilization of the event. All AEs occurring while on study must be documented appropriately regardless of relationship. All AEs will be followed to adequate resolution.

Any medical condition that is present at the time that the participant is screened will be considered as baseline and not reported as an AE. However, if the study participant's condition deteriorates at any time during the study, it will be recorded as an AE.

Changes in the severity of an AE will be documented to allow an assessment of the duration of the event at each level of severity to be performed. AEs characterized as intermittent require documentation of onset and duration of each episode.

The investigator will record all reportable events with start dates occurring any time after informed consent is obtained until 7 (for non-serious AEs) or 30 days (for SAEs) after the last day of study participation. At each study visit, the investigator will inquire about the occurrence of AE/SAEs since the last visit. Events will be followed for outcome information until resolution or stabilization.

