## 5 STUDY POPULATION

## 5.1 INCLUSION CRITERIA

In order to be eligible to participate in this study, an individual must meet all of the following criteria:

- 5.1.1 Tolebrutinib Cohorts Inclusion Criteria
  - 1. Able to provide informed consent
  - 2. Willingness to comply with all study procedures and availability for the duration of the study
  - 3. Male or female, aged  $\geq 18$
  - 4. Diagnosed with multiple sclerosis according to the 2017 revision of the McDonald diagnostic criteria, with no new lesion formation by comparison of baseline MRI scan with a historical MRI scan at least 6 months prior
  - 5. On anti-CD20 antibody treatment for at least 6 months, with the most recent dose at most 6 months prior to enrollment.
  - 6. Willing to forego further anti-CD20 antibody treatment for the duration of the study
  - 7. Fully vaccinated against SARS-CoV-2 by Day 0. At the time of this writing, fully vaccinated is defined as:
    - Two weeks out from the second dose of a two-dose vaccine series (Moderna, Pfizer-BioNTech); or
    - Two weeks out from a single-dose vaccine (Johnson & Johnson/Janssen)

Note: Should guidelines change, we will amend these inclusion criteria accordingly.

- 8. Has a prior 7-tesla MRI scan, no more than 1 year prior to enrollment, demonstrating at least one white matter lesion with a paramagnetic rim^44
- 9. For females of reproductive potential: agrees to use highly effective contraception for at least 1 **month** prior to dosing and to use such a method during study participation and for an additional 12 weeks after the end of tolebrutinib administration
- 10. For males of reproductive potential: agrees to use condoms or other methods to ensure effective contraception with partner; agrees not to donate sperm from the inclusion up to 12 weeks after the last dose
- 11. QuantiFERON-TB Gold negative; skin testing (e.g., tuberculin skin test) will be allowed if blood testing is not available or the blood test result is indeterminate
- 12. Agrees to adhere to Lifestyle Considerations (see section 5.4) throughout study duration
- 13. Agrees not to participate in any other interventional study while participating in this protocol

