## 5.5 LIFESTYLE CONSIDERATIONS

During this study, participants are asked to:

- Tolebrutinib cohorts only.
  - For males of reproductive potential, use condoms or other methods to ensure effective contraception, and not donate sperm from baseline until 12 weeks after the last dose.
  - During the entire study, participants will be advised not to consume substantial quantities of alcohol, defined as >14 grams (1 standard drink) per day in female participants or >28

- grams (2 standard drinks) per day in male participants on a regular basis.
- *All cohorts*. For females of reproductive potential, use highly effective contraception. For the tolebrutinib cohorts, contraception use should last from at least 1 month prior to dosing until 12 weeks after the end of tolebrutinib administration.

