### 7 STUDY INTERVENTION DISCONTINUATION AND PARTICIPANT DISCONTINUA-TION/WITHDRAWAL

### 7.1 DISCONTINUATION OF STUDY INTERVENTION

Participants are free to withdraw from participation in the study at any time upon request.

The PI or MAI may discontinue or withdraw a participant from the study for any of the following reasons:

- Disease activity or progression that requires discontinuation of the study intervention
- If any clinical adverse event (AE), laboratory abnormality, or other medical condition or situation occurs such that continued participation in the study would not be in the best interest of the participant
- Investigator judgment for safety, behavioral, compliance, or administrative reasons
- Positive pregnancy test

The reason for withdrawal or discontinuation will be documented in the medical record. Participants will be asked to return for a follow-up visit within 3 months, and ideally within 1 month after discontinuation of the intervention.

Events of Special Interest (Section 8.4.7) will follow the algorithm outlined in Appendix 2.

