# 8.4.7 Events of Special Interest

The following are defined as Events of Special Interest (ESI). Once identified, they follow the algorithm outlined in Appendix 2 and separate HAC charter.

- Increase in alanine transaminase (ALT) > 3xULN
- Increase in aspartate transaminase (AST) > 3xULN
- Increase in total bilirubin Level (TBL) > 2xULN

Expedited (<15 days) reports will be sent to the FDA for any cases with transaminases >8x ULN or >3x ULN with total bilirubin >2x ULN.

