### 8.4.8 Reporting of Pregnancy

Pregnancy of a female participant as well as pregnancy occurring in a female partner of a male participant is reported as an AE and is qualified and reported as an SAE only if it fulfills one of the seriousness criteria (Section 8.4.2). In the event of pregnancy in a female participant, tolebrutinib should be discontinued. Follow up of the pregnancy in a female participant or in a female partner of a male participant is mandatory until the outcome has been determined.

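### A pregnancy that begins within the protocol's 12-week post-dose contraception period can fall outside the adverse event recording window

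*Combined protocol and SAP*

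**What the plan says.** Four parts of the protocol bear on this.

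- **Recording window (8.4.4).** New events are recorded from consent "until 7 (for non-serious AEs) or 30 days (for SAEs) after the last day of study participation". The limit applies to the start date of an event. Events already recorded are followed until they resolve or stabilise. The last day of participation is not defined relative to the last dose.
- **Pregnancy (8.4.8).** The rule covers participants and the partners of male participants alike. A pregnancy, it says, "is reported as an AE and is qualified and reported as an SAE only if it fulfills one of the seriousness criteria". Once known, it must be followed to its outcome. The section gives no period during which pregnancies are to be sought or notified.
- **Precautions after the last dose (5.1.1 and 5.5).** Women of reproductive potential agree to contraception during the study and "for an additional 12 weeks after the end of tolebrutinib administration". Men of reproductive potential agree to effective contraception, and each "agrees not to donate sperm from the inclusion up to 12 weeks after the last dose". Section 5.5 repeats the period for women: "contraception use should last from at least 1 month prior to dosing until 12 weeks after the end of tolebrutinib administration".
- **Contact after stopping (7.1 and 7.1.1).** "Participants will be asked to return for a follow-up visit within 3 months, and ideally within 1 month" after stopping. After definitive discontinuation, 7.1.1 also provides for an assessment using the Week 24 procedures or those of the next protocol timepoint, but only if possible. The tolebrutinib Schedules of Activities in 1.3 show no post-treatment visit.

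**The concern.** The protocol asks for precautions against pregnancy for 84 days after the last dose. Its recording rule can stop much earlier, and it is counted from a different day. Followed as written, the plan can leave out a pregnancy that begins in a period the protocol itself treats as relevant to pregnancy.

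What would be lost is information the protocol says is lacking. Section 5.4 states that the risk of tolebrutinib in pregnancy and lactation is unknown, and 2.2.4.1 reports variable preclinical effects on pregnancy and embryos. Only 7 participants have been treated, 4 of them at 120 mg (6.1.2.1). The safety analysis in 9.4.4 is a tabulation of recorded events, so a pregnancy that is never recorded cannot appear in it.

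**Working it through.** The plan states no figure to reproduce. The check is day arithmetic on its own periods.

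**Inputs**
- Recording limit for a non-serious event: 7 days after the last day of participation (8.4.4).
- Class of an uncomplicated pregnancy: non-serious adverse event (8.4.8).
- Post-dose precaution period: 12 weeks = 12 × 7 = 84 days, counted from the last dose (5.1.1, 5.5).
- Follow-up visit after stopping: within 3 months, ideally within 1 month (7.1). Assumed here to be 90 and 30 days.

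**Formula.** Let L be the number of days from the last dose to the last day of participation. Recording ends on day L + 7 after the last dose. The uncovered part of the precaution period is max(0, 84 − (L + 7)) = max(0, 77 − L).

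| Last day of participation | L (days) | Recording ends (day) | Uncovered days of 84 |
|---|---|---|---|
| Day of last dose | 0 | 7 | 77 |
| Follow-up visit at about 1 month | 30 | 37 | 47 |
| Follow-up visit at about 3 months | 90 | 97 | 0 |

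The gap closes only if L is at least 77 days. The visit timing that 7.1 prefers leaves 47 of 84 days uncovered, or 56%.

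**Does 7.1.1 close the gap?** It names the procedures to use but does not clearly fix the date. Suppose it means the date of the next scheduled timepoint, and that this visit then counts as the last day of participation. Where visits are 12 weeks apart, L reaches 77 days only for someone who stops within 84 − 77 = 7 days after a visit, ignoring visit windows. In the extension, with visits every 24 weeks (168 days), it does so for someone who stops within 168 − 77 = 91 days after a visit. Coverage therefore depends on when the participant stops and on whether the assessment takes place.

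**The case against.** The strongest reply is that pregnancy has its own rule. Section 8.4.8 makes follow-up to outcome mandatory with no time limit, and 8.4.4 does not forbid recording a pregnancy that is reported late. Sections 7.1 and 7.1.1 both provide for an assessment after stopping, and the main on-treatment visits from Week 12 onwards include a pregnancy test. With a follow-up visit at about 3 months there is no gap at all.

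Much of this stands. A known pregnancy must be followed, so it would be wrong to say that follow-up cannot begin for one reported late. The 77-day figure is the upper end of the range, not the expected case. But mandatory follow-up presupposes that someone has learned of the pregnancy, and nothing obliges anyone to ask through the 12 weeks. The visit in 7.1 is a request, preferably held early, and the assessment in 7.1.1 is conditional. Neither schedules a pregnancy test for a male participant's partner. If 8.4.8 is meant to have no time limit, it disagrees with 8.4.4 and the two still need reconciling.

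It is also fair to say that the practical reach is small. The secondary safety objective covers defined treatment periods, so pregnancies after a long extension bear on the safety record more than on that objective. A participant who moves to marketed drug may have no post-dose period. The documents do not say how many of the 7 are of reproductive potential.

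A reader might go further and infer that 12 weeks is a general risk period, so that liver events such as "Increase in alanine transaminase (ALT) > 3xULN" and all serious events are also under-collected against an 84-day standard. The documents do not support this. The 12 weeks appears only as a period for contraception and sperm donation. Section 8.4.7 and Appendix 2 set no post-dose period for liver events that the 7-day limit would contradict, and no such period is set for serious events in general.

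**Conclusion.** The point holds for pregnancies. An uncomplicated pregnancy in a participant or partner that starts within the protocol's own 12-week post-dose precaution period can fall outside the recording window. The uncovered part runs from 0 to 77 days and is about 47 days at the follow-up timing the protocol prefers.

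This rests on three readings: that an uncomplicated pregnancy is governed by the limit for non-serious events, that the follow-up visit is the last day of participation when it takes place, and that 1 and 3 months are 30 and 90 days. The first follows from 8.4.4 and 8.4.8 together. The second is an assumption, because the term is undefined, and that ambiguity is itself part of the problem.

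The conclusion is limited to the recording of pregnancies. It does not show that the windows for liver events or serious events are too short, and it says nothing about whether 12 weeks is the right length for the precautions.

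**What to change.** Reconcile 8.4.4, 8.4.8, 7.1 and 5.5 on the anchor and length of the window for pregnancies:

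- In 8.4.4, state that in the tolebrutinib cohorts a pregnancy in a participant or a male participant's partner is recorded if it starts up to 12 weeks after the last tolebrutinib dose, or up to the present limit if that is later. Define the last day of participation.
- In 8.4.8, refer to that window, so that the duty to follow a pregnancy and the duty to record it cover the same cases.
- In 7.1 and the Schedules of Activities, add one telephone contact at the end of the 12 weeks for participants who stop tolebrutinib. A pregnancy that began late in the period may not yet be recognised at the call, so participants should be asked to report one found afterwards.

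This uses the protocol's existing 12-week figure and changes only data collection. The cost is amended wording, one call for each of at most 7 participants, and slightly later closure of their safety records.
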